**Table 11**                      **Definition of Severity of Adverse Events**

Severity	Description
Severe	Grade 3 – Interferes significantly with the patient’s usual function (incapacity to work or to do usual activities (unacceptable).
Life-threatening	Grade 4 – Results in risk of death, organ damage or permanent disability (unacceptable)
Death	Grade 5 – Event has a fatal outcome

Note: It is important to distinguish between serious and severe AEs. Severity is a measure of intensity whereas seriousness is defined by the criteria in Section 7.3.2. An AE of severe intensity need not necessarily be considered serious. For example, nausea that persists for several hours may be considered severe nausea, but not a SAE. On the other hand, a stroke that results in only a limited degree of disability may be considered a mild stroke but would be a SAE

A copy of the CTCAE version can be downloaded from the Cancer Therapy Evaluation Program website (<http://ctep.cancer.gov>)

### **Causality**

The Investigator will assess causal relationship between Investigational Product and AEs, and answer “yes” or “no” to the question “Do you consider that there is a reasonable possibility that the event may have been caused by the investigational product?”

Note that for SAEs that could be associated with any study procedure the causal relationship is implied as “yes”.

A guide to the interpretation of the causality question is found in [Appendix B](#) to the Clinical Study Protocol.

#### **7.3.3.2 Adverse Events based on signs and symptoms**

All AEs spontaneously reported by the subject or reported in response to the open question from the study personnel: “Have you had any health problems since the previous visit?” or revealed by observation will be collected and recorded in the CRF. When collecting AEs, the recording of diagnoses is preferred (when possible) to recording a list of signs and symptoms. However, if a diagnosis is known and there are other signs or symptoms that are not generally part of the diagnosis, the diagnosis and each sign or symptom will be recorded separately.

#### **7.3.3.3 Adverse Events based on examinations and tests**

Deterioration as compared to baseline in protocol-mandated laboratory values, vital signs and other safety variables will only be reported as AEs if they fulfil any of the SAE criteria or are the reason for stopping treatment with the investigational product. If a deterioration in a laboratory value/vital sign is associated with clinical signs and symptoms, the sign/symptom will be reported as an AE and the associated laboratory result/vital sign will be considered as

additional information. Any new or aggravated clinically relevant abnormal medical finding at a physical examination as compared with the baseline assessment will be reported as an AE.

Clinically relevant deterioration in non-protocol-mandated measurements will be reported as AE(s).

Wherever possible the reporting Investigator uses the clinical, rather than the laboratory term (eg, anaemia versus low haemoglobin value).

#### **7.3.3.4 Disease progression**

Disease progression can be considered as a worsening of a patient's condition attributable to the type of cancer for which the study drugs are being studied. It may be an increase in the severity of the cancer or an increase in the symptoms of the cancer. Expected progression of the patient's cancer and/or expected progression of signs and symptoms of the cancer, unless more severe in intensity or more frequent than expected for the patient's condition, should not be reported as an AE. Any events that are unequivocally due to progression of disease must not be reported as an AE.

The development of new metastases, or progression of existing metastases to the primary cancer under study, should be considered as disease progression and not an AE. Signs and symptoms clearly associated with metastases present at study entry should not be reported as AEs unless they are newly emergent (ie, not previously observed in the patient), judged by the Investigator to be unusually severe or accelerated, or if the Investigator considers deterioration of disease related signs and symptoms to be caused directly by the study medication.

#### **7.3.3.5 New cancers**

The development of a new primary cancer should be regarded as an AE and will generally meet at least one of the serious criteria (see Section 7.3.2). New primary cancers are those that are not the primary reason for the administration of the study treatment and have developed after the inclusion of the patient into the study. They do not include metastases of the original cancer. Symptoms of metastasis or the metastasis itself should not be reported as an AE/SAE, as they are considered to be disease progression.

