## Continued Supply Expansion Phase (including dose escalation groups)

- **Primary outcome variable**

- Safety (all patients): AEs, physical examination, vital signs including BP, pulse and body temperature ECG and laboratory findings including clinical chemistry, haematology and urinalysis.

- **Secondary outcome variables**

- The following single dose PK parameters will be derived for the Melt Extrusion (tablet) formulation and the Gelucire® 44/14 (capsule) formulation:  $C_{max}$ ,  $C_{min}$  and  $AUC_{0-8}$  (Group 8 tds schedule),  $AUC_{0-12}$  (all patients on bd schedule) and  $AUC_{0-24}$  (Group 8 od schedule).
- The following multiple dose PK parameters will be derived for the Melt Extrusion (tablet) formulation and the Gelucire® 44/14 (capsule) formulation:  $C_{ss,max}$ ,  $C_{ss,min}$  and  $AUC_{ss}$
- Efficacy: change from baseline in the sum of target lesions (as per RECIST), Progression-Free Survival (PFS), best overall response, CA-125 response
- Preliminary assessment of the effect of food on the exposure of AZD2281 tablet (Group 8 patients only) – Day 8 : Day 1  $C_{max}$  and  $AUC_{0-24}$  ratios

- **Exploratory outcome variables**

- Exploratory biomarker analysis of the activity of AZD2281 and correlation with disease progression/response to therapy will be conducted. If available, archival tumour samples from patients enrolled Group 6, 7 and 8 will be collected in order to achieve this objective.

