#### **6.1.1 Procedures for randomisation**

Eligible patients will be randomised in a 1:1 ratio (Sequence 1: Sequence 2) for Cohorts 1, 2 and 3 and Group 2 of the Continued Supply Expansion Phase. The actual treatment sequence given to individual patients will be determined by separate randomisation schemes for each cohort.

Eligible patients will be randomised in a 1:1 ratio (Treatment A: Treatment B) for Group 1 of the Continued Supply Expansion Phase.

Eligible patients will be randomised in a 1:1 or 1:1:1 ratio (Treatment A: Treatment B: and Treatment C (if applicable)) for Group 6 of the Continued Supply Expansion Phase.

Eligible patients will be randomised in a 1:1:1:1 ratio (Schedule A: Schedule B: Schedule C: Schedule D) for Group 8, Randomised Tablet Formulation Continued Supply Expansion Phase.

A blocked randomisation will be generated and all centres will use the same list in order to minimise any imbalance in the number of patients assigned to each treatment group. The randomisation scheme will not be stratified for the randomisation of treatment sequences. However, the randomisation of treatment arms for Group 1, 6 and 7 patients in the Continued Supply Expansion Phase will be stratified according to primary tumour type (either breast cancer or ovarian cancer). For Group 6 and 7 both gBRCA breast and gBRCA ovarian patients will be randomised. However, there should be at least 10 gBRCA ovarian patients enrolled per treatment arm; therefore recruitment may be closed to non-ovarian cancer patients before ovarian cancer patients.

Patient eligibility will be established before treatment randomisation. Patients will be randomised strictly consecutively, as patients are eligible for randomisation. Once the eligibility of a patient has been confirmed, the Investigator (or nominated assistant) should contact the Centralised Randomisation Centre by telephone for allocation of randomised treatment sequence or treatment arm and randomisation number. Patients will be identified to the Centralised Randomisation Centre using patient initials, enrolment number and date of birth and which Group the patient is intended to be randomised in to. The Centralised Randomisation Centre will inform the Investigator of the treatment sequence or treatment arm to be allocated to the patient at the randomisation visit.

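### Section 7.3.3.5 bars, without exception, symptoms of metastasis that Section 7.3.3.4 makes reportable as adverse events in three stated cases

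*Protocol*

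**What the plan says.** Section 7.3.3.4 (Disease progression) has two paragraphs. The first exempts expected progression and its expected symptoms from AE reporting, except where they are more severe or more frequent than expected for that patient. It closes with an absolute sentence: "Any events that are unequivocally due to progression of disease must not be reported as an AE".

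The second paragraph treats new metastases, and progression of existing ones, as disease progression. It then sets a rule for symptoms: "Signs and symptoms clearly associated with metastases present at study entry should not be reported as AEs unless they are newly emergent". Two more exceptions follow: the investigator judges the symptoms unusually severe or accelerated, or "if the Investigator considers deterioration of disease related signs and symptoms to be caused directly by the study medication".

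Section 7.3.3.5 (New cancers) says that a new primary cancer is an AE and that metastases of the original cancer do not count as new primaries. Its last sentence is: "Symptoms of metastasis or the metastasis itself should not be reported as an AE/SAE, as they are considered to be disease progression".

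For the expansion phase, including the dose escalation groups, the synopsis gives the primary outcome as "Safety (all patients): AEs, physical examination, vital signs including BP, pulse and body temperature ECG and laboratory findings". Section 12.6.2 summarises AEs by treatment. Section 6.1.1 states: "The Centralised Randomisation Centre will inform the Investigator of the treatment sequence or treatment arm to be allocated to the patient".

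**The concern.** A site that meets a new symptom from a metastasis known at baseline finds two instructions on adjoining topics that give opposite answers, and nothing says which one governs. A site that follows 7.3.3.5 as written drops events that 7.3.3.4 asks for. These include disease-related symptoms whose worsening the investigator attributes to the drug, which are the events of most interest for a safety profile.

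Two things are at stake. The first is completeness of safety reporting. In-patient hospitalisation makes an AE serious (Section 7.3.2), and SAEs must reach the sponsor by the end of the next business day (Section 7.3.3.11), so an admission for such a symptom is reportable under one section and not under the other. The second is comparability. AE counts are set side by side by formulation, dose or schedule in Groups 1, 6, 7 and 8, and the person who classifies each event knows the allocation.

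**Working it through.** The protocol gives no figure on this point, so the check is a comparison of text followed by a statement of scale.

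**Step 1: apply each rule to the same events.** All rows concern the original cancer.

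| Event | 7.3.3.4, second paragraph | 7.3.3.4, last sentence of first paragraph | 7.3.3.5, last sentence |
|---|---|---|---|
| New symptom clearly from a metastasis present at entry | AE | Not an AE if unequivocally due to progression | Neither AE nor SAE |
| Symptom of such a metastasis, unusually severe or accelerating | AE | Not an AE if unequivocally due to progression, although the sentence before it spares symptoms worse or more frequent than expected | Neither AE nor SAE |
| Disease symptom whose worsening is attributed directly to the drug | AE | Does not bite: the event is not unequivocally due to progression | Neither AE nor SAE, read literally |
| Known symptom of such a metastasis, expected course | Not an AE | Not an AE | Neither AE nor SAE |
| Appearance of a new metastasis, or growth of a known one | Not an AE | Not an AE | Neither AE nor SAE |

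The second paragraph of 7.3.3.4 and the last sentence of 7.3.3.5 agree in the last two rows and disagree in the first three. The direct conflict is thus confined to symptoms of metastases present at entry that fall under one of the three exceptions. Within 7.3.3.4, the absolute sentence can clash with the exceptions in the first two rows.

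**Step 2: look for a rule of precedence.** Section 7.3.3.5 does not refer to 7.3.3.4, and neither section ranks the two.

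**Step 3: trace the events into the outcome.** An AE that meets a criterion in 7.3.2 is an SAE, so the conflict carries over to SAE counts. AEs come first in the primary safety outcome and are tabulated by treatment. The protocol uses the term open-label for the PK Phase (Section 4.1.1). For the randomised expansion groups, knowledge of the arm follows from the disclosure in Section 6.1.1.

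**Step 4: scale of one reclassified patient.** Arm sizes follow from the planned numbers and randomisation ratios:

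- Group 1: 20 patients, 1:1, gives 20/2 = 10 per arm; 1/10 = 10 percentage points.
- Group 6: about 45, 1:1:1, gives 45/3 = 15 per arm.
- Group 7: about 30, 1:1, gives 30/2 = 15 per arm.
- Group 8: about 60, 1:1:1:1, gives 60/4 = 15 per arm.
- Groups 6 to 8: 1/15 = 6.7 percentage points.

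These steps apply to the incidence of a given term, and only if the patient has no other report of that term. How many patients would be affected cannot be derived, because the protocol gives no rate for such symptoms.

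**The case against.** The best defence is that 7.3.3.5 concerns new cancers, and that its last sentence only explains why a metastasis is not a new primary. On that reading the phrase about disease progression sends the reader back to 7.3.3.4, which holds the detailed rule, and the defect is a missing cross-reference. This is how the sponsor may have meant it, but the text does not say so. The sentence before already separates metastases from new primaries. The last sentence goes further, with a general instruction on symptoms that extends to SAEs. Site staff cannot be expected to infer that it is subordinate.

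Other parts of the defence stand. Section 7.3.3.5 says should not, which is weaker than a prohibition. Section 7.3.3.6 separately keeps a deterioration from being written off as lack of efficacy when the sponsor or physician thinks treatment contributed, so a drug-attributed event has support in two sections. Safety is descriptive, so no test or error rate is affected. Dose-limiting toxicities must be possibly or probably drug-related (Section 6.2.4.3), so symptoms clearly due to metastasis should not drive escalation. AEs are also only one of several primary safety variables.

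A reader might infer more than this, in three ways that the document does not support:

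- That Section 7.3.3.3 adds another contradiction, because it makes new or aggravated findings at physical examination AEs with no exemption for disease. That is a general rule followed by a specific one for disease-related events, which is ordinary drafting.
- That the counts of nausea, vomiting and fatigue are broadly compromised, because these are named drug effects and could also be disease symptoms. The exclusion in 7.3.3.4 needs a clear link to metastases, and many such events in treated patients will not meet that test.
- That a sizeable spurious difference between arms can be projected. This would need a symptom rate and a degree of differential classification by arm. The protocol gives neither, and nothing in it shows investigators choosing a section by arm.

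**Conclusion.** The contradiction is real, narrow and cheap to remove. It concerns symptoms of metastases present at entry that are new, unusually severe or accelerating, or attributed to the drug. Section 7.3.3.4 makes them AEs and 7.3.3.5, read literally, makes them neither AEs nor SAEs. The absolute sentence in 7.3.3.4 adds a lesser inconsistency.

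Its effect is on AE and SAE counts, and on the comparability of those counts between arms whose allocation the investigator knows. The total effect is unknown; the per-patient steps in the working show only that arms of 10 to 15 leave little room for inconsistent classification. The case for correction does not depend on any assumed event rate or on bias between arms: it is enough that events which one section asks for would be lost by following the other. The correction should be made, but the finding does not call the design or the planned analysis into question.

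**What to change.** Reconcile the passages with two edits.

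1. In Section 7.3.3.5, delete the last sentence, or open it with a clause making it subject to the exceptions in Section 7.3.3.4. Deletion loses nothing, since the sentence before it already keeps metastases apart from new primaries.
2. In Section 7.3.3.4, state that the sentence on events unequivocally due to progression is subject to the exceptions in that section.

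The cost is two clauses in an amendment and a note to sites. No change to the CRF, the visits, the patient numbers or the planned tables is needed. Sites that had been applying 7.3.3.5 literally may record some more AEs and SAEs, which 7.3.3.4 already asks for. Recording every symptom whatever its cause, with a new field for progression, would be a change of AE policy and is not needed to remove the contradiction.

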#### **7.3.3.6 Lack of efficacy**

When there is deterioration in the condition for which the study treatment(s) is being used, there may be uncertainty as to whether this is lack of efficacy or an AE. In such cases, unless the Sponsor or the reporting physician considers that the study treatment contributed to the deterioration of the condition, or local regulations state to the contrary, the deterioration should be considered to be a lack of efficacy and not an AE.

#### **7.3.3.7 Deaths**

All deaths that occur during the study, or within the protocol-defined 30-day post-study follow-up period after the administration of the last dose of study treatment, must be reported as follows:

- 
- Death clearly the result of disease progression should be reported to the study monitor at the next monitoring visit and should be documented in the CRF but should not be reported as an SAE.
  - Where death is not due (or not clearly due) to progression of the disease under study, the AE causing the death must be reported to the study monitor as a SAE within **24 hours** (see Section 7.3.2 for further details). The report should contain a comment regarding the co-involvement of progression of disease, if appropriate, and should assign main and contributory causes of death. This information can be captured in the ‘death CRF’.
  - Deaths with an unknown cause should always be reported as a SAE. A post mortem maybe helpful in the assessment of the cause of death, and if performed a copy of the post-mortem results should be forwarded to AstraZeneca Patient Safety Department within the usual timeframes.

#### **7.3.3.8 Overdose**

Should an overdose (accidental or deliberate) occur, it must be reported in accordance with the procedures described in Section 1.2, Procedures in case of overdose, regardless of whether the overdose was associated with any symptom or not. All symptoms associated with the overdose should be reported as AEs.

#### **7.3.3.9 Pregnancy**

Should a pregnancy occur, it must be reported in accordance with the procedures described in Section 1.3. Procedures in case of pregnancy. Pregnancy in itself is not regarded as an AE unless there is a suspicion that an investigational product may have interfered with the effectiveness of a contraceptive medication.

[figure not shown]
#### **7.3.3.10 Follow-up of unresolved adverse events**

Any AEs/SAEs that are unresolved at the patient’s last AE assessment (ie, 7 or 30 day follow up visit) in the study are followed up by the Investigator for as long as medically indicated. After data cut-off, any ongoing AEs will be recorded as ongoing. AstraZeneca retains the right to request additional information for any patient with ongoing AE(s)/SAE(s) at the end of the study, if judged necessary.

#### **7.3.3.11 Reporting of serious adverse events**

All SAEs have to be reported, whether or not considered causally related to the study treatment, or to the study procedure(s). All SAEs will be recorded in the CRF. SAEs will be recorded from the time of informed consent.

The Investigator and/or Sponsor are responsible for informing the Ethics Committee and/or the Regulatory Authority of the SAE as per local requirements.

For studies in countries implementing the European Union (EU) Clinical Trials Directive, informing Ethics Committees and Regulatory Authorities will be performed by AstraZeneca. If any SAE occurs in the course of the study, then Investigators or other site personnel inform appropriate AstraZeneca representatives immediately but no later than the end of the next business day of when he or she becomes aware of it.

For fatal or life-threatening AEs where important or relevant information is missing, active follow-up is undertaken immediately. Investigators or other site personnel inform appropriate AstraZeneca representatives of any follow-up information on a previously reported SAE immediately but no later than the end of the next **business day** of when he or she becomes aware of it.

Investigators or other site personnel send relevant CRF modules by fax to the designated AstraZeneca representative and any other relevant supporting documentation (eg, ECG, laboratory results, autopsy report).

The designated AstraZeneca representative works with the Investigator to ensure that all the necessary information is provided to the appropriate AstraZeneca Patient Safety data entry site within **one business day** for fatal and life threatening events and within **five calendar days** for other SAEs. If the report arrives late in the day, it can be sent the following morning. If the report arrives during a weekend or public holiday, the information is forwarded as early as possible on the first business day following the weekend or holiday. The clock start date is then the next business day.

The reference document for definition of expectedness/listedness is the IB for the AstraZeneca drug.

#### **7.3.4 Laboratory safety assessment**

Full haematology assessments for safety (haemoglobin, red blood cells [RBC], platelets, mean corpuscular volume [MCV], mean corpuscular haemoglobin concentration [MCHC], mean corpuscular haemoglobin [MCH], WBC, differential white cell count (neutrophils, lymphocytes, monocytes, eosinophils and basophils), ANC, and coagulation [APTT and international normalised ratio {INR}]) will be performed.

Biochemistry assessments for safety (sodium, potassium, calcium, magnesium, chloride, glucose, creatinine, total bilirubin, gamma glutamyltransferase [GGT], alkaline phosphatase [ALP], AST, ALT, urea, total protein, albumin, lactic dehydrogenase [LDH]) will be performed.

These tests will be performed by the hospital's local laboratory. Additional analyses may be performed if clinically indicated.

For blood volume see Section [8.1](#).

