From the completed studies, there are no safety concerns noted for the renal or hepatic parameters measured and no clinically significant changes of concern relating to coagulation parameters. The changes in haematological parameters (haemoglobin, neutrophils, and thrombocytes) are as expected for monotherapy AZD2281 or can be explained by co-existing conditions/previous chemotherapy. Preliminary data from Phase I and Phase II studies of AZD2281 in combination with various chemotherapy agents indicate an increase in neutropenia, thrombocytopenia and anaemia compared to giving these agents alone. These findings are consistent with pre-clinical findings and are reflected in the more severe haematological events ie, CTCAE grade 4 neutropenia, febrile neutropenia and thrombocytopenia being reported as SAEs.

Final laboratory data from D0810C00002 (KU36-92) study has shown MCV increases in approximately 30% of patients in the study, especially with prolonged treatment with AZD2281 ( $\geq 6$  cycles of treatment). The MCV elevations were mild to moderate in intensity, observed in the 200 mg bid dose cohort and above and were asymptomatic in nature. There was no obvious correlation of MCV with haemoglobin, platelets or WBC values for these patients, and there does not appear to be any clinical consequences. MCV has not been captured as a standard laboratory parameter within the AZD2281 Phase II studies D0810C00008 (KU36-44) and D0810C00009 (KU36-58), however elevations in MCV were also observed in a number of patients from these studies. The MCV elevations again appear to become progressively elevated over time. MCV has been included in many of the ongoing studies and will be included in future study protocols to allow further safety investigation.

Elevations in serum amylase were observed in approximately 15% of patients from final laboratory study data from D0810C00002 (KU36-92). The majority of these increases (13%) were mild to moderate (CTCAE grade 1 or 2) with no apparent link to clinical symptoms. The impact of AZD2281 on amylase and lipase is unclear and the parameters have been incorporated into ongoing protocols and will be measured in future protocols to allow further investigation. No new significant safety information has emerged from any other reported studies with respect to elevations in serum amylase.

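### Amylase and lipase, which section 2.1.5 says are being added to the programme's protocols, are missing from this trial's biochemistry list, so no group has them measured systematically

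*Protocol*

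**What the plan says.** The clinical background (Protocol, section 2.1.5) states: "Elevations in serum amylase were observed in approximately 15% of patients from final laboratory study data", referring to study D0810C00002. On severity it adds: "The majority of these increases (13%) were mild to moderate (CTCAE grade 1 or 2) with no apparent link to clinical symptoms". It then says that "The impact of AZD2281 on amylase and lipase is unclear" and that "the parameters have been incorporated into ongoing protocols and will be measured in future protocols to allow further investigation". The paragraph closes by noting that other reported studies have brought no new significant safety information on amylase.

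Section 7.3.4 sets out what the laboratory will measure. The list opens "Biochemistry assessments for safety (sodium, potassium, calcium, magnesium, chloride, glucose, creatinine, total bilirubin, gamma glutamyltransferase [GGT" and finishes "alkaline phosphatase [ALP], AST, ALT, urea, total protein, albumin, lactic dehydrogenase [LDH]) will be performed". It is written as a complete list, with no wording that marks it as a set of examples. Further tests are allowed only when clinically indicated. The study schedules (Tables 5, 6 and 7) refer simply to haematology and clinical chemistry, so section 7.3.4 alone decides which analytes are run.

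**The concern.** The background treats amylase and lipase as an open question that the programme's protocols are meant to follow up. This protocol's own panel does not measure them and gives no reason. Safety is the primary objective of the expansion phase, and clinical chemistry is a named safety variable for Groups 1 to 8 (section 3.1, Table 2).

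Two things are at stake. First, elevations without symptoms would not be found at scheduled visits, and the rises the protocol describes as mild to moderate had no apparent link to symptoms. Second, drug-related non-haematological grade 3/4 toxicity can count as a dose limiting toxicity (section 6.2.4.3), and two such patients in an escalation group make the dose not tolerable (section 4.1.2.3). A silent grade 3/4 enzyme rise that could bear on that judgement would not come before the Safety Review Committee unless someone had ordered the test. The gap is in data collection, so a statistical analysis plan cannot repair it later.

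**Working it through.** The protocol gives no sample size, power or error-rate figure on this point, so there is none to reproduce. The check compares the sections and adds a short calculation for scale.

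**Step 1: the two sections side by side.**

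| Item | Section 2.1.5 | Section 7.3.4 |
|---|---|---|
| Amylase | About 15% raised in one study; in ongoing protocols, to be measured in future ones | Not listed |
| Lipase | Effect unclear; same statement | Not listed |
| MCV | In many ongoing studies, to be included in future ones | Listed under haematology |

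The biochemistry list has 16 entries: sodium, potassium, calcium, magnesium, chloride, glucose, creatinine, total bilirubin, GGT, ALP, AST, ALT, urea, total protein, albumin and LDH. Neither analyte is mentioned anywhere in the protocol outside section 2.1.5. The MCV row shows that one of two parallel statements reached the panel and the other did not.

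**Step 2: can another route detect a rise?** Section 7.3.4 allows clinically indicated tests. Section 7.3.3.3 has clinically relevant deterioration in measurements the protocol does not mandate reported as adverse events. Both depend on someone first ordering the test. For an elevation without symptoms there is usually no prompt.

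**Step 3: scale, assuming the earlier study's 15% applies here.** Expected number = n × 0.15. Chance of at least one = 1 − 0.85^n.

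- Escalation group of 6 (the minimum, section 4.1.2.3): 6 × 0.15 = 0.9 expected; 1 − 0.85^6 = 62%.
- Arm of about 15 (section 12.4.5): 15 × 0.15 = 2.25 expected; 1 − 0.85^15 = 91%.
- Group 8, about 60 patients: 60 × 0.15 = 9 expected.

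Subtracting the grade 1–2 share from the total leaves 15% − 13% = about 2% above grade 2, or 60 × 0.02 = 1.2 patients in Group 8. The 15% is itself approximate, so this residual is very uncertain and should not be relied on.

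**Step 4: what measured values could show.** If 2 of 15 patients in an arm had an elevation, the exact 95% confidence interval would be 1.7% to 40%. If the true rates in two arms of 15 were 15% and 30%, a two-sided Fisher exact test at the 5% level would have about 8% power. Arms of this size allow description and detection in individual patients, not a reliable comparison.

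**The case against.** The strongest case on the other side has four parts.

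- **The statement is about the programme.** Section 2.1.5 speaks of ongoing and future protocols without saying all of them or naming this one. The study was expected to start in October 2008 (section 10.5) and the clinical experience is dated 20 November 2009, so the likeliest explanation is background text that was updated without carrying the change into section 7.3.4. This stands: it is an inconsistency to reconcile, not a broken promise specific to this trial. But the trial was itself ongoing when the background was written, and MCV was carried through.

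- **The evidence of a problem is modest.** The 15% comes from one study, other reported studies added nothing significant, and amylase is not in the list of effects that section 2.1.5 associates with the drug. This also stands. A reader might infer evidence of harm; the document does not support that.

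- **The analytes are not wholly unmonitored.** A reader might infer that no elevation could ever be recorded. That goes too far, because the clinically indicated route exists. The absence of symptoms is also stated only for the 13% with grade 1–2 rises; nothing is said about the more severe ones, which might prompt a test. What remains is that detection is left to chance ordering.

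- **Measuring them would not settle the exposure question.** A reader might see this trial as the place to learn whether amylase changes with dose or schedule. Safety is summarised descriptively, and Step 4 shows that the arms are too small for such a comparison. This stands in full. The case for measuring rests on individual detection and description.

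**Conclusion.** The inconsistency is real and of moderate weight. Section 2.1.5 says amylase and lipase are being followed up; section 7.3.4 does not measure them, and nothing explains why. As written, neither is systematically measured in any group, and an elevation without symptoms, including a grade 3/4 rise relevant to the dose limiting toxicity assessment, would not be detected by the scheduled panel.

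A reader might place the gap only at the higher tablet doses. It applies to every group; its consequence is sharpest in the escalation groups because the tolerability decision is made there.

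The figure of about 9 in 60 for Group 8 assumes that the earlier study's rate carries over. The protocol does not say at which doses those rises occurred or whether they were new on treatment, so the figure indicates scale only. The finding that the two sections do not match needs no such assumption.

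**What to change.** Reconcile sections 2.1.5 and 7.3.4. The preferred change is to add amylase and lipase to the biochemistry list in section 7.3.4, measured at the visits where clinical chemistry is already drawn (Tables 6 and 7), with a baseline value for every patient not yet dosed, and to include both in the CTCAE shift tables of section 12.6.2. If the sponsor has decided not to collect them in this trial, section 2.1.5 should say so and give the reason; that would also remove the inconsistency, though not the gap in detection.

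The cost is two extra assays at the local laboratory alongside chemistry samples already being taken, and a CRF field for each. Patients already on treatment would have no pre-treatment value, so their results could be described but not expressed as a shift from baseline.
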